6.4.2. Solicited Adverse Events

A solicited AE is a predetermined event which may reflect safety concerns related to the IP. The solicited AEs for this study include:

Local Events:

• Redness, swelling, or pain at site of injection

Systemic Events:

- Subjective or objective fever
- Chills
- Sweats
- Myalgia (described to the subject as generalized muscle aches)
- Fatigue
- Gastrointestinal symptoms (nausea, vomiting, abdominal pain, and/or diarrhea)

Rheumatologic Events:

- Arthralgia (described to the subject as generalized joint aches/pain [general or while moving joints]); affected joints will be captured
- Joint swelling
- Joint tenderness

Dermatologic Events:

- Mouth ulcer
- Skin or mucosal lesion (rash, blister, ulcer)

Neurologic Events:

Blurry vision, changes in balance or coordination, confusion, disorientation, dizziness, severe
headache, shaking or body tremors, slurred speech, tingling or numbness, weakness or feeling
weak

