3. STUDY DESIGN

3.1. STUDY ENDPOINTS

3.1.1. Primary Safety Endpoints

- Incidence and severity of solicited injection site AEs (arm pain, local tenderness, erythema (redness), induration (swelling/firmness) and systemic AEs (objective fever, subjective fever, chills, sweats, headache, myalgia, arthralgia, fatigue, nausea, vomiting) and neurological AEs (blurry vision, changes in balance or coordination, confusion, disorientation, dizziness, severe headache, shaking or body tremors, slurred speech, tingling or numbness, weakness or feeling weak) between days 1 and 8, and days 9-15 after vaccination, per treatment group (active vaccination versus placebo) and stratified by relatedness.
- Incidence and severity of unsolicited AEs between days 1-8, days 9-15, and up to day 29 after vaccination, per treatment group (active vaccination versus placebo) and stratified by relatedness.
- Incidence and severity of arthritis and skin/mucosal lesions up to day 29 after vaccination using standard case definitions and stratified by relatedness. This includes where possible quantitative reverse transcription polymerase chain reaction (RT-qPCR) for detection of PHV01 and lesion biopsy for histopathology.
- Incidence of SAEs observed up to day 181 and stratified by relatedness.
- Incidence and severity of MAAEs observed up to day 181 and stratified by relatedness.
- Physical and neurological examination results, vital signs, normal and abnormal clinical laboratory values (hematology and clinical chemistry, urinalysis).
- Incidence of adverse events of special interest (AESIs), to include pneumonitis, acute respiratory distress syndrome, multiorgan failure, a hemorrhagic diathesis, certain neurologic events (encephalitis, myelitis, aseptic meningitis, optic neuritis, transverse myelitis, generalized convulsions, Guillain-Barré Syndrome, acute disseminated encephalomyelitis), thrombocytopenia, anaphylaxis, and vasculitides.

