3.1.3. Safety Endpoint Collection

Safety will be assessed by analysis of the occurrence of TEAE and vaccinemia, as well as by adverse changes in laboratory evaluations (chemistry, hematology, urinalysis), vital signs, and physical including neurologic examinations. All AEs will be collected systematically through day 29 (Section 1.5.1). SAEs, MAAEs, and AESIs will be collected for the entire period each participant is on study with the help of Memory Aides, reviewed at the day 29, 85, and 181 visits.

AEs will be coded according to Medical Dictionary of Regulatory Activities (MedDRA) Version 26.1 (or latest) (36). A TEAE is defined as an AE that starts or worsens on or after the date and time of the study vaccination. AE endpoints include:

• Solicited TEAEs.

- O Solicited local AEs (at the injection site) are reported daily through day 14 and systemic reactogenicity symptoms, facilitated through the use of a memory aid, occurring from vaccination through 15 days following vaccination. *Note: solicited AEs for days 16-29 are limited to instances of neurological signs and symptoms, arthritis, and rash.*
- o Local reactogenicity signs and symptoms, including arm pain, local tenderness, erythema (redness), and induration (swelling/firmness).
- O Systemic reactogenicity signs and symptoms, including subjective and objective fever, shivering/chills, sweats, myalgia (generalized muscle aches), arthralgia (joint aches/pain, general or while moving joints; affected joints will be captured), joint swelling, joint tenderness, fatigue, gastrointestinal symptoms (nausea, vomiting, abdominal pain, and diarrhea), mucosal lesion (any sores or lesions, including mouth ulcers), skin lesion (including any rashes or blisters), and neurological symptoms (blurry vision, changes in balance or coordination, confusion, disorientation, dizziness, severe headache, shaking or body tremors, slurred speech, tingling or numbness, weakness or feeling weak). As noted in this paragraph, a severe headache is an adverse event that may represent a potential neurologic AESI.

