7.5.1. Analysis Addressing the Primary Study Objective (Safety)

Solicited symptoms occurring during the 28 days following vaccination will be summarized by treatment group and by relatedness. The incidence and severity of solicited AEs to the vaccine over the 28-day follow-up period will be calculated. Presentations will include the number and percentage of subjects with at least 1 local AE, and at least 1 general (systemic) AE, as well as the incidence of each AE individually.

The number of subjects with at least 1 incidence of an unsolicited AE reported up to 28 days after vaccination will also be summarized overall and by treatment group. The severity and temporal relationship of the unsolicited AEs to vaccination will also be assessed. Presentations will also summarize unsolicited AEs by grade and vaccine-relatedness. Serious AEs occurring at any point during the trial will be summarized and relatedness to vaccine will be assessed. The incidence rate of solicited AEs may be compared between each treatment group and placebo using Fisher's exact test and logistic regression.

The level of vaccinemia (on days 1 [at 0 and 6 hours], 2, 4, 8, 15, and 29) and shedding will be assessed on all subjects. The proportion of subjects with detected vaccinemia, as well as the geometric mean and AUC of vaccinemia level, will be presented at each time point where data are collected. The relationship between vaccinemia level and dose will be explored in a mixed model for repeated measures (MMRM) analysis that incorporates dose level, time, and other potential predictive factors. A similar model will be used to explore the relationship between dose and the AUC of the vaccinemia level.

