4.4.2. Adverse Events

AEs will be assessed by evaluating reactogenicity (local reactions and systemic reactions) and the occurrence of post-vaccination solicited local reactions and systemic AEs through day 15. Solicited AEs for days 16-29 are limited to instances of neurological signs and symptoms, arthritis, and rash. Arthritis, rash, and neurologic events should be evaluated throughout the study and may include expert consultation.

All AEs (including solicited AEs) will be coded using the MedDRA coding system and displayed in tables and data listings using system organ class (SOC) and preferred term (PT). Note that solicited and unsolicited AEs will be analyzed and presented separately. The severity of all AEs will be graded in accordance with the FDA document "Guidance for Industry: Toxicity Grading Scale for Healthy Adult and Adolescent Volunteers Enrolled in Preventive Vaccine Clinical Trials" described in Section 5.

Analyses of AEs will be performed for those events that are considered treatment-emergent, where treatment-emergent is defined per protocol as any AE with onset after the administration of study medication.

All AEs occurring on-study will be listed in subject data listings.

By-subject listings also will be provided for the following: subject deaths, SAEs, AEs leading to withdrawal, solicited local site AEs, solicited systemic AEs, MAAEs, and AESIs.

Solicited AEs are predefined local events at the injection site and systemic events for which the subject is specifically questioned and facilitated by use of memory aides.

The following local AEs will be solicited:

- Arm Pain [CRF term: Pain at Site of Injection]
- Local Tenderness [CRF term: Tenderness at Site of Injection]
- Erythema (Redness) [CRF term: Redness at Site of Injection]
- Induration (Swelling/Firmness) [CRF term: Swelling at Site of Injection]

Note: CRF term in the square brackets refers to the term used on the Adverse Event Case Report Form to capture the local solicited AEs.

The following systemic (non-injection site) AEs will be solicited:

- Subjective Fever [CRF term: Subjective Fever]
- Objective Fever [CRF term: Fever]
- Chills [CRF term: Chills]
- Sweats [CRF term: Sweats]
- Myalgia [CRF term: Myalgia]
- Arthralgia [CRF term: Arthralgia]
- Joint Swelling [CRF term: Joint Swelling]
- Joint Tenderness [CRF term: Joint Tenderness]
- Fatigue [CRF term: Fatigue]

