- Gastrointestinal Symptoms (symptoms include nausea, vomiting, abdominal pain, and diarrhea) [CRF terms: Nausea, Vomiting, Abdominal Pain, Diarrhea]
- Mucosal Lesions [CRF terms: Mucosal Lesion, Mouth Ulcer]
- Skin Lesions [CRF terms: Skin Lesion]
- Neurological Symptoms (symptoms include blurry vision, changes in balance or coordination, confusion, disorientation, dizziness, severe headache, shaking or body tremors, slurred speech, tingling or numbness, weakness or feeling weak) [CRF terms: Blurry Vision, Changes in Balance or Coordination, Confusion, Disorientation, Dizziness, Severe Headache, Shaking or Body Tremors, Slurred Speech, Tingling or Numbness, Weakness or Feeling Weak]

Neurological symptoms described above will be considered as solicited neurological AEs. Specific joint related (arthralgia, joint swelling, and joint tenderness) will be considered as solicited rheumatologic AEs; and mouth ulcer or skin/mucosal lesions will be considered as dermatologic AEs.

All TEAEs that cause a subject to seek medical care (including extra visits to the clinical site) are considered to be MAAEs.

Additionally, certain neurologic/hematologic/immunologic diseases are considered as AESIs in the study. Such AESIs include pneumonitis, acute respiratory distress syndrome, multiorgan failure, a hemorrhagic diathesis, certain neurologic events (encephalitis, myelitis, aseptic meningitis, optic neuritis, transverse myelitis, generalized convulsions, Guillain-Barré Syndrome, acute disseminated encephalomyelitis), thrombocytopenia ≥ Grade 2, anaphylaxis, and vasculitides.

Summary tables will be generated for the following:

- Solicited local site AEs within 7 days, and 8 to 14 days following vaccination by Solicited Term and severity
- Solicited systemic AEs within 7 days, and 8 to 14 days following vaccination by Solicited Term and severity
- Solicited neurological AEs within 7 days, 8 to 14 days, 15 to 28 days and up to day 181 following vaccination by Solicited Term and severity
- Unsolicited AEs within 7 days, 8 to 14 days, 15 to 28 days and up to day 181 following vaccination by SOC, PT, relatedness, and severity

- Solicited Rheumatologic AEs within 28 days and up to day 181 following vaccination by Solicited Term and severity
- Solicited Dermatologic AEs within 28 days and up to day 181 following vaccination by Solicited Term and severity
- SAEs up to day 181 by SOC, PT and relatedness
- MAAEs up to day 181 by SOC, PT and relatedness

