- AESIs at baseline, and up to day 181 by SOC, PT and relatedness

The number and percentage of subjects with any AE type as described above will be summarized by treatment group and combined PHV01 group. Adverse events are summarized by subject incidence rates; therefore, in these tabulations, each subject will contribute once (i.e., the most related occurrence or the most intense occurrence) to each of the incidence rates in the analysis regardless of the number of episodes. Tabulation by relatedness to study vaccine will be categorized as Related (Definite, Probable, Possible) or Not related; while tabulation by severity will be graded as Grade 1 (Mild), Grade 2 (Moderate), Grade 3 (Severe), Grade 4 (Potentially life-threatening).

Additionally, a symptom score will also be used to summarize solicited local and systemic AEs. The symptom score is a scalar quantity that summarizes the overall severity of a subject's solicited AE experience. The symptom index for a given AE will be defined as individual unique toxicity grades reported for each TEAE multiplied by the duration of the TEAE. The individual symptom indices will then be summed for each subject to obtain their symptom score. Larger scores are indicative, overall, of more severe and/or AEs of longer duration; smaller scores are indicative, overall, of less severe and/or AEs of shorter duration.

If an AE is ongoing at the end of the observation period, the length of the observation period post vaccination will be used in the calculation of symptom index. If the severity is missing for any particular AE, then the corresponding symptom index will also be set to missing.

Symptom scores will be summarized descriptively by treatment group and the combined PHV01 treatment group. Symptom scores will be calculated separately for all solicited local and systemic AEs which started within 14 Days of vaccination. The mean, standard deviation, median, minimum, and maximum values will be tabulated.

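### Solicited 'systemic' adverse events are defined by three conflicting lists, and the SAP does not say which one feeds the any-systemic rate, the symptom score and its viremia correlation

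*Protocol*

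**What the plan says.** The documents group the solicited events that are not at the injection site in three ways.

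- **Set A.** Protocol 3.1.1 (primary safety endpoints) names "systemic AEs (objective fever, subjective fever, chills, sweats, headache, myalgia, arthralgia, fatigue, nausea, vomiting) and neurological AEs" as two groups. SAP 1.2.5.1 repeats the same ten systemic terms.
- **Set B.** Protocol 6.4.2 has a systemic heading with ten terms and separate rheumatologic, dermatologic and neurologic headings. Arthralgia is in the rheumatologic group: "Arthralgia (described to the subject as generalized joint aches/pain [general or while moving joints]); affected joints will be captured".
- **Set C.** Protocol 3.1.3 opens its broad list with "Systemic reactogenicity signs and symptoms, including subjective and objective fever, shivering/chills, sweats, myalgia (generalized muscle aches), arthralgia" and continues through joint, gastrointestinal, mucosal, skin and neurological symptoms. SAP 4.4.2 does the same under "The following systemic (non-injection site) AEs will be solicited", with the CRF term beside each entry.

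After its list, SAP 4.4.2 regroups: "Neurological symptoms described above will be considered as solicited neurological AEs". It treats the joint terms likewise as rheumatologic and the mouth, skin and mucosal terms as dermatologic. It then plans a systemic table alongside separate neurological, rheumatologic and dermatologic tables.

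Three outputs use the word 'systemic' without a term list. Protocol 7.5.1 reports subjects with "at least 1 general (systemic) AE". SAP 4.4.2 builds a severity-by-duration score: "Symptom scores will be calculated separately for all solicited local and systemic AEs which started within 14 Days of vaccination". SAP 4.4.4 correlates viremia AUC with the index for systemic events.

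**The concern.** The any-systemic rate and the systemic symptom score are the composite reactogenicity summaries by dose. Solicited events also feed the day 29 interim analysis that guides dose selection for the next trial (Protocol 7.2, SAP 3.12). If the protocol, the SAP text and the table programs each use a different set, one label covers different quantities. Two programmers could both follow the SAP faithfully and produce different rates, scores and correlations.

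On the literal SAP list, a joint episode in the first two weeks is counted in both the systemic and the rheumatologic tables. It can also enter the systemic score under up to three terms: arthralgia, joint swelling and joint tenderness. On the regrouped list it enters neither the systemic table nor the systemic score.

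A second gap concerns a named component of the primary endpoint. Plain headache is in set A and has its own row in the systemic grading tables (Protocol Appendix 1 Table A2, SAP Table 5-2). It is not among the solicited terms in Protocol 3.1.3, Protocol 6.4.2 or SAP 4.4.2, which list only severe headache, as a neurological symptom.

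**Working it through.** The documents state no term count, so there is no planned figure to reproduce. I counted terms and compared the sets.

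| Source | Set | Terms | Headache | Arthralgia | Abdominal pain, diarrhea | Joint signs, skin/mucosal, neurological |
|---|---|---|---|---|---|---|
| Protocol 3.1.1, SAP 1.2.5.1 | A | 10 | yes | yes | no | no |
| Protocol 6.4.2, systemic heading | B | 10 | no | no | yes | no |
| Protocol 3.1.3 | C | 25 | severe only | yes | yes | yes |
| SAP 4.4.2, systemic heading | C | 26 | severe only | yes | yes | yes |

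**Comparison of sets.**
- A and B share 8 terms. Headache and arthralgia are only in A; abdominal pain and diarrhea are only in B.
- Protocol 3.1.3: the 10 terms of B + 3 joint + 2 skin/mucosal + 10 neurological = 25.
- SAP 4.4.2 has 26 because mouth ulcer is its own CRF term. Protocol 3.1.3 already includes mouth ulcers within mucosal lesion, so the content is the same. The any-systemic rate is identical under both. A summed score could differ only if one lesion were recorded under both CRF terms.
- B lies wholly inside C. A does not, because plain headache is missing from C.
- SAP regrouping: 26 - 10 neurological - 3 joint - 3 mouth/skin/mucosal = 10, and these ten are exactly B.

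**Effect on the rate.** Group sizes are 10 per dose and 6 placebo (Protocol 7.1). One subject whose only qualifying event lies in a disputed class moves the rate by 1/10 = 10 points in a dose group, or 1/6 = 16.7 points in placebo.

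**Effect on the score.** The index is grade × duration, summed over terms. Protocol 1.5.1 gives arthritis after the related Ebola vaccine a median onset of 12 days (IQR 10-14) and a median duration of 8 days (IQR 6-15), so onset often falls inside the score's 14-day window. Assume one Grade 2 episode with the same duration under each term used:
- three joint terms, 8 days: 3 × 2 × 8 = 48 points for the subject, and 48/10 = 4.8 on the mean of a group of 10;
- range from one term for 6 days (1 × 2 × 6 = 12) to three terms for 15 days (3 × 2 × 15 = 90), or 1.2 to 9.0 on the group mean;
- under set B: 0.

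**Direction of the contrast.** Assume any-systemic rates of 70% (vaccine) and 30% (placebo) on the narrow list. Let each of the 16 extra terms occur independently with probability q. The rate on the broad list is then 1 - (1 - p)(1 - q)^16.
- q = 2% in both arms: 78% v 49%, 29 points.
- q = 5% in both arms: 87% v 69%, 18 points.
- q = 5% in vaccinees and 1% in placebo: 86.8% v 40.4%, 46 points.

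The starting contrast is 40 points, so it narrows or widens according to an assumption that the documents do not settle.

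**The case against.** The strongest reply is that the SAP already points to one reading. It relabels the neurological, joint and skin terms immediately after the broad list, gives each class its own table, and leaves exactly the ten systemic terms of Protocol 6.4.2. For the systemic table this is the natural interpretation, and that much stands.

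It does not settle the other outputs. SAP 4.4.2 elsewhere divides solicited events into local and systemic only, plans dedicated by-subject solicited listings for just those two, and computes scores for just those two. On the narrow reading, joint, skin and neurological events enter no score; on the broad reading, they enter the systemic score as well as their own tables. The text supports both.

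The reply is also right that the stakes are limited. The score is descriptive, SAP 3.2 confines formal testing to immunogenicity, and Protocol 7.5.1 makes comparison of solicited rates with placebo optional. Events are also tabulated by individual term and by time window, so individual terms and their timing remain visible.

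A reader might infer more than the documents support:
- That there are four definitions. The 25- and 26-term lists have the same content.
- That the broad list shrinks the vaccine-placebo contrast. This needs equal extra rates in both arms. For the related vaccine, Protocol 1.5.1 reports higher rates in vaccinees than in controls for arthritis (4.5% v 3.2%) and dermatitis (5.7% v 3.2%). Independence among joint terms is also doubtful.
- That Protocol 6.4.2 can serve unchanged as the master list. It lacks plain headache and, among local events, tenderness.
- That mild headache will go unrecorded. It could still be reported as an unsolicited event, and the CRF itself is not among the documents.

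**Conclusion.** The inconsistency is real and concerns a primary safety summary. There are three sets, and no passage states which one defines the any-systemic rate, the systemic symptom score or its correlation with viremia AUC. The term counts and the 10- and 16.7-point steps follow directly from the documents. The 48-point example assumes a Grade 2 episode entered under three terms, with a duration taken from a different vaccine. No size or direction can be given for the change in the vaccine-placebo contrast, because the documents contain no per-term rates for PHV01. The headache gap is separate and equally checkable: a named primary-endpoint component has a grading row but no solicited term except in its severe form. The point merits correction before the tables are programmed. It does not threaten the trial's validity.

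**What to change.** In SAP 4.4.2, add a mapping that assigns every solicited CRF term to exactly one class: local, systemic, rheumatologic, dermatologic or neurologic. State that the any-systemic rate, the systemic symptom score and its correlation with viremia AUC use the systemic class only. Add a separate row for any solicited event away from the injection site, so that the union remains reported.

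Reconcile Protocol 3.1.1, 3.1.3 and 6.4.2 and SAP 1.2.5.1 to that mapping, keeping headache and local tenderness. State where non-severe headache is captured and in which table it appears.

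The cost is a SAP wording and table-shell edit with a short protocol clarification. A headache CRF term may also be needed if none exists. One consequence should be accepted openly: events outside the local and systemic classes would enter neither symptom score and would be seen in their own tables and in the union row.

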6.4.3. Adverse Events of Special Interest

The following are AESIs that will be monitored with increased frequency for safety purposes. AESIs that meet the serious criteria as defined in Section 6.4.4 will be reported as SAEs.

Respiratory Events:

• Acute respiratory distress syndrome/pneumonitis

Neurologic Events:

- ADEM
- Aseptic meningitis
- Encephalitis
- Generalized convulsions
- GBS
- Myelitis
 - o Optic neuritis
 - Transverse myelitis

Hematologic Events:

• Thrombocytopenia ≥ Grade 2

Immunologic Events:

- Anaphylaxis
- Vasculitides

